6.5.4 Prior Specification (Secondary Count Outcomes)

For the intercept and the encephalopathy terms, Normal(mean = 0, sd=1) priors will be used.

For any other covariates added to the model for sensitivity analyses or any exploratory model, a Normal(mean=0, sd=1) prior will be used.

For the random center effect, we will assume a normal distribution centered at 0, and the standard deviation parameter will be assumed to follow a half-normal hyperprior with mean equal to 0 and standard deviation equal to 1.

For the term representing the log mean ratio of hypothermia a neutral prior will be used to estimate posterior distributions for the mean ratio. Because the negative binomial model will estimate the log rate ratio as the treatment parameter, the priors for the treatment effect will be normal priors on the log scale. These normal priors for the log rate ratio are defined below so that the resulting priors in the mean ratio scale have specified properties.

On the mean ratio scale, the neutral prior for the mean rate will be centered at 1.0 and have a 95% credible interval with an approximate range of 0.33 to 3.0. This neutral prior will be defined by a normal prior on the log mean ratio scale centered at 0 with standard deviation (SD) of 0.5605, Normal(mean = 0, sd=0.5605).

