4.1 Modeling Processes, Prior Specification, and Reporting Procedures

- For binary outcomes, the protocol specified that a Bayesian log-binomial regression model with random center effect would be fit to estimate the relative risk of hypothermia relative to normothermia. However, since the protocol was written, an increasing emphasis has been placed on including inference on risk differences in clinical trial reports, so a logistic regression model with random center effect will be fit followed by post-processing of individual predicted probabilities of outcome to estimate posteriors of relative risk and risk differences.¹
 - Weakly informative priors will be used during analyses to better understand the effect of hypothermia on outcomes considered in this trial:
 - On the relative risk and risk difference scales of primary outcome and components, the priors for the treatment effect will include a skeptical prior, a neutral prior, and an enthusiastic prior. For all other outcomes, only the neutral prior will be used.
 - For the intercept and the encephalopathy terms, broad neutral priors will be used.
 - For the random center effect, a Normal prior centered at 0 will be used where the standard deviation parameter of this prior will have a half-normal hyperprior with mean equal to 0 and standard deviation equal to 1.
 - Further details about these priors are given in section 6.4.2 and 6.4.3
 - Posterior distributions, posterior means, posterior probabilities of benefit, and 95% credible intervals will be reported for the effect of hypothermia on the outcomes considered.
- For count outcomes such as days or durations, a negative binomial model with random center effect will be fit to estimate relative risk.
 - Weakly informative priors will be used during analyses to better understand the effect of hypothermia on outcomes considered in this trial:
 - On the relative risk scale, the priors for the treatment effect will include a neutral prior.
 - For the intercept and the encephalopathy terms, broad neutral priors will be used.
 - For the random center effect, a Normal prior centered at 0 will be used where the standard deviation parameter of this prior will have a half-normal hyperprior with mean equal to 0 and standard deviation equal to 1.
 - Further details about these priors are given in section 6.4.2 and 6.4.3

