6.3 Hospital Course Outcomes

Hospital Course outcomes that may be considered in analysis are:

- Proven NEC (*Binary, PH13, G.4, if PH13PNEC = 2 or 3.*)
- Spontaneous Intestinal perforation without proven NEC (SIP) (*Binary, PH13: G.5, PH13GAST, if PH13GAST = ‘Y’*)

⁵ Subcutaneous fat necrosis may occur after 108 hours.

- seizures after beginning of assigned treatment {Clinical Seizures} (Binary, PH13: D.1.b, D.1.c, D.1.d, D.1.e, taken from PH13SZAB, or PH13SZDM, or PH13SZRW, or PH13SZNT equal to 'Y')
- culture-positive bloodstream or infection of other normally sterile site at >3 days (Binary, PH13: E.1, E.2, PH13SEPT or PH13MENG needs to be 'Y')
- persistent pulmonary hypertension (PPHN) after start of intervention period (Binary, PH13: B.2, PH13PPHN)
- metabolic abnormalities after start of intervention period (Binary, PH13: I.1, I.2, I.3, I.4, I.5, I.6, I.7, PH13HYGL = 'Y' or PH13HYRG = 'Y' or PH13HYCA = 'Y' or PH13HYMA = 'Y' or PH13HYKA = 'Y' or PH13HYRK = 'Y' or PH13HYPH = 'Y')
- treatment with vasopressors and/or steroids after start of intervention period (Binary, PH13: C.7, PH13INOV)
- oliguria after start of intervention period (Binary, PH13: F.1, PH13OLIG)
- anuria after start of intervention period (Binary, PH13: F.2, PH13ANUR)
- liver dysfunction after start of intervention period (AST>200 IU and/or ALT>100 IU) (Binary, PH13: G.7, PH13EAST)
- liver dysfunction after start of intervention period (elevated direct bilirubin) (Binary, PH13: G.8, PH13EDBR)
- clinically diagnosed coagulopathy after start of intervention period (Binary, PH13: H.1, PH13DIC)
- days receiving oxygen/mechanical ventilation (Continuous, PH13: B.6, B.7, B.8, based on PH13DVEN and PH13DOXY, and PH13DCPA)
- Ventilation (Binary, if days receiving oxygen/mechanical ventilation > 0 then = yes)
- duration of NICU stay among survivors (Continuous, PH13: R.1, PH13DSDT (date of discharge) minus PH05: A.1.a, PH5BRTDT (birthdate))
- Bowel perforation (multi-level, = 'NEC' if PH13 G4 = 2, = 'NEC with Perforation' if PH13 G4 = 3, = 'SIP if PH13 G5 = 'Y')
- neurological injury by cranial ultrasound within 24 hours of enrollment, identified by local reader (Binary, PH12, see sub-section Analysis of Ultrasound, CT scan, MRI and encephalopathy outcomes under section 6.5.5.)
- Abnormal neurological examination at discharge
- Death prior to discharge

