$$trt_{ij} = \begin{cases} 0 & \text{normothermia} \\ 1 & \text{whole body hypothermia} \end{cases}$$

$$enceph_{ij} = \begin{cases} 0 & \text{mild encephalopathy} \\ 1 & \text{moderate or severe encephalopathy} \end{cases}$$

The model used for analysis of day and duration outcomes will have the following form:

$$y_{ij} \sim \text{NegBinomial}[\vartheta_{ij}], \text{ where}$$

$$\ln(\vartheta_{ij}) = \alpha_i + \theta_1 \cdot enceph_{ij} + \theta_2 \cdot trt_{ij}$$

β_1, β_2 will have priors as specified in Section 6.5.4

α_i will be the random intercepts due to center. Prior specified in Section 6.5.4.

The prior for the random center effects will be Gaussian centered at 0, and the hyperprior for the standard deviation of the random center effect will be specified in Section 6.5.4. Any baseline covariates that are added to the model (in sensitivity analyses) will either be coded using 0/1 indicator variables, sets of indicator variables, or as centered continuous covariates. Priors for these other to-be-determined covariates are specified in Section 6.5.4.

The analysis of ordinal outcomes will use sets of logistic regression models as used for binary outcomes. One of the ordinal outcome levels will be designated as the reference level, and then logistic regression models will be fit to subsets of the data where one group of included data will be records that equal to reference level and the other group of included data will be records that equal one of the other outcome levels. For example, if an ordinal outcome has 3 levels, with level 3 designated as the reference level, then two logistic regression models will be fit:

- One model will use data from level 1 and level 3
- The second model will use data from level 2 and level 3

The prior for the random center effects will be Normal centered at 0, and the hyperprior for the standard deviation of the random center effect will be specified in Section 6.5.3. Any baseline covariates that are added to the model (in sensitivity analyses) will either be coded using 0/1 indicator variables, sets of indicator variables, or as centered continuous covariates. Priors for these other to-be-determined covariates are specified in Section 6.5.3.

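### The Normal(0, 1) intercept prior for the count models is not broad on a log-days scale; with 0/1 treatment coding it slightly inflates the rate ratio if mean durations are well above one day

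*SAP*

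**What the plan says.** Section 4.1 introduces the priors for count outcomes as weakly informative and then says: "For the intercept and the encephalopathy terms, broad neutral priors will be used". Section 6.5.4 supplies the number: "For the intercept and the encephalopathy terms, Normal(mean = 0, sd=1) priors will be used". This is the same prior as section 6.5.3 gives for the logistic models.

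Section 6.5.1 introduces the count model with "The model used for analysis of day and duration outcomes will have the following form" and sets the log of the mean equal to a center intercept plus an encephalopathy term plus a treatment term. Treatment is coded 0 for normothermia and 1 for hypothermia. The day and duration outcomes in section 6.3 are "days receiving oxygen/mechanical ventilation" and "duration of NICU stay among survivors". Both are on a list of outcomes that may be analyzed.

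The treatment coefficient has a "normal prior on the log mean ratio scale centered at 0 with standard deviation (SD) of 0.5605", described as giving a "95% credible interval with an approximate range of 0.33 to 3.0". Section 6.5.5 summarizes count outcomes by the rate ratio, its credible interval and the probability that the ratio is below 1. For count-type safety outcomes it reports the probability that the ratio is above 1, read as harm. Only the neutral treatment prior is used for these outcomes, and no sensitivity analysis on the intercept prior is planned.

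**The concern.** A standard deviation of 1 covers a wide span of risks on the logit scale, but on the log-days scale it is a statement about duration. Its median is one day. Section 3.2 describes a 72-hour intervention and an MRI at 10 to 17 days of age, or before discharge or transfer if that comes sooner. A survivor who completes the intervention has stayed at least three days, yet 86% of the prior mass lies below a mean of three days.

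With reference-cell coding, the intercept and the treatment coefficient are negatively correlated in the posterior. A prior that pulls the intercept down therefore pushes the treatment coefficient up. The treatment prior is centered on a ratio of 1 and presented as neutral, but the analysis as a whole would lean slightly toward longer durations under hypothermia. The planned output would not reveal this.

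**Working it through.** **1. The plan's own figure.** Treatment prior, Normal(0, 0.5605): exp(±1.96 × 0.5605) = 0.333 to 3.000. The stated 0.33 to 3.0 is reproduced.

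**2. The intercept prior on the same footing.** exp(±1.96 × 1) = 0.141 to 7.10 days. The prior probability that the reference mean exceeds m days is 1 - Φ(ln m): 13.6% for 3 days, 1.1% for 10, 0.42% for 14, 0.14% for 20 and 0.03% for 30. Adding the center effect widens the center-level range to about 0.06 to 17 days, but in the fits below the center effects did not absorb the shift.

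**3. Approximate size.** Take 84 infants per arm (168/2), mean m and negative binomial shape k. The variance of one arm's log mean is about v = (1/k + 1/m)/84. With the SAP's treatment prior variance s² = 0.5605² = 0.314, an intercept prior of SD 1 moves the log rate ratio, relative to a flat intercept prior, by about

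ln(m) × v × s²/(s² + 2v).

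- m = 20, k = 1.5: 3.00 × (0.717/84) × 0.95 = +0.024
- m = 10, k = 0.7: 2.30 × (1.529/84) × 0.90 = +0.038
- m = 20, k = 1: 3.00 × (1.05/84) × 0.93 = +0.035

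MCMC fits comparing intercept SD 1 with SD 10 gave +0.026 for the first case and +0.036 for the second. The sign follows ln(m), so the shift is upward only when the mean exceeds one day.

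**4. Simulation with all other SAP priors kept.** From the SAP: 168 infants, 18 centers, half-normal(SD 1) hyperprior for the center SD. Assumed, because the SAP gives none: mean duration, k, 25% severe encephalopathy, true center SD 0.2, and 120 infants for a survivors-only outcome. Encephalopathy is coded moderate versus severe. Each data set was fitted with intercept SD 1 and SD 10 by a Laplace approximation integrated over center SD and dispersion. Results are averages.

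| Mean (days) | k | n | True ratio | Estimated ratio, SD 1 ÷ SD 10 | Pr(ratio < 1), SD 1 vs SD 10 |
|---|---|---|---|---|---|
| 5 | 3 | 168 | 1 | 1.010 | 0.437 vs 0.460 |
| 5 | 1 | 168 | 1 | 1.021 | 0.504 vs 0.543 |
| 5 | 0.5 | 168 | 1 | 1.034 | 0.372 vs 0.418 |
| 10 | 0.5 | 168 | 1 | 1.049 | 0.409 vs 0.467 |
| 20 | 3 | 168 | 1 | 1.014 | 0.473 vs 0.506 |
| 20 | 1 | 168 | 1 | 1.036 | 0.422 vs 0.497 |
| 30 | 1 | 168 | 1 | 1.040 | 0.440 vs 0.514 |
| 20 | 3 | 120 | 1 | 1.020 | 0.457 vs 0.509 |
| 20 | 1 | 120 | 1 | 1.050 | 0.356 vs 0.427 |
| 20 | 1 | 168 | 0.8 | 1.036 | 0.754 vs 0.802 |
| 20 | 3 | 168 | 0.8 | 1.013 | 0.922 vs 0.934 |
| 0.5 | 1 | 168 | 1 | 0.980 | 0.573 vs 0.547 |

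**5. Encephalopathy coding as printed.** Section 6.5.1 codes mild as 0 and moderate or severe as 1. Section 5.1 admits only moderate to severe encephalopathy, so every infant has value 1 and the normothermia log mean is the intercept plus the encephalopathy term. Its prior SD is √2 = 1.41, and the 95% range is 0.06 to 16 days. The prior variance doubles, so the shift roughly halves. At k = 1 and n = 168 the ratio of estimates was 1.010 at 5 days and 1.017 at 20 days, against 1.021 and 1.036 above.

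**6. Treatment coding.** With treatment coded ±0.5 and the SD 1 prior kept, the average shift in the log ratio was at most 0.001. The bias comes from the prior and the reference-cell coding together.

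**The case against.** Section 4.1 puts its wording under a statement that priors are weakly informative and refers onward for detail; 6.5.4 then gives an exact number. An analyst would know what to fit. That stands: the wording is a poor description of the prior, not an ambiguity in the instruction.

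The effect is also small. It is roughly 0.05 to 0.27 of a posterior SD, so a 95% interval barely moves, and no threshold or decision depends on these probabilities. That stands too.

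A reader might infer that the prior biases every day or duration outcome against hypothermia. The documents do not support this. They give no expected durations, and the direction depends on the mean exceeding one day. Days of oxygen or ventilation could average within 0.14 to 7.1 days, where the shift is smaller: at an assumed mean of 2 days it was about +0.01 on the log ratio.

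Finally, the larger figures need moderate-versus-severe coding, which is not what 6.5.1 prints. Section 3.3 stratifies by moderate versus severe, so the printed coding is probably itself an error. Correcting it would restore the full effect.

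**Conclusion.** The point holds in a limited form. On a log-mean scale, Normal(0, 1) is informative about duration and does not match its description in 4.1. Combined with 0/1 treatment coding, it moves the rate ratio upward, against hypothermia, if mean durations are well above one day. With moderate-versus-severe coding and assumed means of 5 to 30 days, the shift averages about 1 to 5% on the ratio. The loss in Pr(ratio < 1) averages about 0.02 to 0.08 when the true ratio is 1, and was 0.01 to 0.05 in the fits with a true ratio of 0.8. Both shifts are about half as large under the printed encephalopathy coding.

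These sizes rest on assumed means, dispersion and center variation; the SAP also states no prior for the dispersion parameter. It would be wrong to conclude that this prior could decide a trial result. It affects only secondary or hospital-course count outcomes, and the primary and other binary outcomes are outside this point. It is a minor, avoidable bias.

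**What to change.** In section 6.5.4, give the intercept of the log-link models a genuinely broad prior, for example Normal(0, sd = 5). This changes one number and makes 6.5.4 match 4.1.

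Alternatively, keep the prior and code treatment as ±0.5 in the count models. Section 6.5.8 already uses effect coding for its interaction models. In that case, reword 4.1, because the intercept prior would still not be broad.

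Either way, leave the Normal(0, 0.5605) treatment prior as it is. Centering the intercept prior on the log of the pooled observed mean would also work, but it takes the prior from the trial's own outcome data and is less clean. The cost is a short entry in the SAP revision history and, if the count models have already been run, a refit. The encephalopathy coding in 6.5.1 should be reconciled with the stratification in 3.3 at the same time, since it determines how large this effect is.

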6.5.5 Final Analysis

The final analysis will occur after 168 infants have completed the trial, as specified earlier. The final analysis will not occur until all enrolled infants have a primary outcome determination, i.e. have the primary endpoint value assigned, classified as withdrawn without primary outcome assigned, or deemed lost to follow-up. Part of determining primary outcome of enrolled infants will involve masked adjudication of outcomes for infants who have an indeterminable outcome based on partially collected follow-up information. Once all enrolled infants have reached final status and primary endpoints determined, the clinical database will be exported, and study analysis datasets created. At that point, the analysis datasets will be considered “locked” and any further adjustments to the clinical datasets will not be included in the analysis datasets.

The final analysis will involve posterior distribution estimation for the effect of hypothermia relative to normal cooling. For binary outcomes, the effect will be the adjusted relative risk and adjusted risk differences calculated from a binomial regression model with logit link and post processing of

predicted outcome probabilities. For count outcomes, the effect will be the adjusted relative risk from the two groups obtained using negative binomial regression. For ordinal outcomes, the effect will be the adjusted odds ratio calculated from the cumulative logits.

For treatment relative risk estimation, posterior probabilities of >0%, >5%, >10% and >20% decrease in binary outcomes will be calculated. If θ is the relative risk defined as risk in cooling group over risk in control group, then the above specified posterior probabilities are, $\Pr(\theta < 1 | X)$, $\Pr(\theta < 0.95 | X)$, $\Pr(\theta < 0.9 | X)$, $\Pr(\theta < 0.8 | X)$. In addition to posterior probability calculations, graphical displays of the posterior distribution and appropriate 95% credible intervals for the over-all relative risk will be created. Finally, forest plots of the center level relative risks and 95% credible intervals will be created.

In addition to adjusting for level of encephalopathy and center in the logistic model, the final analysis of the primary outcome will also perform sensitivity analyses concerning possible treatment effect confounders present at randomization. These sensitivity analyses will adjust for baseline covariates that differ across the two treatments in addition to adjusting for level of encephalopathy and center. The additional covariates will be determined by comparing the primary outcome with respect to baseline characteristics listed in Section 5.3. More details about these sensitivity analyses are given in section 6.5.7. Secondary analyses may also adjust for covariates, but in such a case the analysis will only be completed with covariate adjustment. No secondary analyses will be completed twice, in the sense of one analysis without covariates and another analysis with covariates. These analyses will use the FAS population.

The lack of preexisting data suggests that the neutral prior distribution may be most appropriate for presentation of final results; however, generation of final results of the primary outcome analysis using the skeptical (RR of 1.10) and enthusiastic priors (RR of 0.75) will also be produced for the primary outcome to give a broad overview of the implications of the trial's efficacy results. Skeptical, neutral, and enthusiastic priors will also be utilized in the analysis of primary outcome components. All non-primary or non-primary component outcomes will be analyzed using only the neutral prior.

For treatment risk difference estimation, posterior probabilities of >0%, >1%, >2%, >3%, and >5% decrease in binary outcomes will be calculated (corresponding to NNTs of 100, 50, 33, and 20). If ψ is the risk difference defined as risk in normothermia group minus risk in cooling group, then the above specified posterior probabilities are, $\Pr(\psi < 0 | X)$, $\Pr(\psi < 0.01 | X)$, $\Pr(\psi < 0.02 | X)$, $\Pr(\psi < 0.03 | X)$, and $\Pr(\psi < 0.05 | X)$. In addition to posterior probability calculations, graphical displays of the posterior distribution and appropriate 95% credible intervals for the over-all risk difference will be created. Finally, forest plots of the center level risk differences and 95% credible intervals will be created.

In addition to adjusting for level of encephalopathy and center in the logistic model, the final analysis of the primary outcome will also perform sensitivity analyses concerning possible treatment effect confounders present at randomization. These sensitivity analyses will adjust for potential treatment effect confounders in addition to adjusting for level of encephalopathy and center. The additional covariates will be determined by comparing the primary outcome with respect to baseline characteristics listed in Section 5.3. More details about these sensitivity analyses are given in section 6.5.7. Secondary analyses may also adjust for covariates, but in such a case the analysis will only be completed with covariate adjustment. No secondary analyses will be completed twice,

in the sense of one analysis without covariates and another analysis with covariates. These analyses will use the FAS population.

The lack of preexisting data suggests that the neutral prior distribution may be most appropriate for presentation of final results of risk differences; however, generation of final results of the primary outcome analysis using the skeptical (OR of 1.10) and enthusiastic priors (OR of 0.75) will also be produced for the primary outcome to give a broad overview of the implications of the trial's efficacy results. Note, these priors are expressed on the OR scale, because the underlying model is a logistic regression model and posteriors of risk difference will be generated via post-processing. Skeptical, neutral, and enthusiastic priors will also be utilized in the analysis of primary outcome components. All non-primary or non-primary component outcomes will be analyzed using only the neutral prior.

For treatment rate ratios of count outcomes estimation, the posterior of the treatment rate ratio, ϕ , will be graphically illustrated and summarized by calculating the median treatment rate ratio, the 95% credible interval of treatment rate ratio, and $\Pr(\phi < 1 | X)$ using neutral priors. These analyses will use the FAS population.

Primary Analysis of Primary Outcome

With respect to the primary outcome, the data will be analyzed using the FAS population.

In summary the following analyses will be completed on the primary outcome:

Population	FAS					
Treatment effect	RR			RD		
Prior*	E	N	S	E	N	S

* E = Enthusiastic, N = Neutral, S = Skeptical

Each of the six analyses of the primary outcome will generate the following results:

- Posterior plot of treatment effect
- Posterior median and posterior standard deviation
- 95% credible interval
- For relative risk, posterior probabilities of >0%, >5%, >10%, and >20% decrease in the primary outcome will be calculated
- For risk difference, posterior probabilities of >0%, >1%, >2%, >3%, and >5% decrease in primary outcome will be calculated
- forest plot of the center level effect and 95% credible intervals.

If the FAS analysis of the primary outcome results in any clinically notable findings, then the primary outcome may also be analyzed in an exploratory fashion using the PP population.

Analysis of Secondary Outcomes

With respect to secondary outcomes, analyses will follow the same process as the primary outcome analysis defined above. See MockTablesAppendix.docx for list of selected variables.

Analysis of Safety (AE) and Hospital Outcomes

Safety and hospital outcomes listed in Sections 6.2 and 6.3 will be analyzed using the FAS population and if necessary, the PP population using relative risk models, proportional odds models, or Negative Binomial models, depending on the type of outcome.

With respect to binary safety outcomes, the estimated posterior distribution of relative risk, θ , based on the data and the neutral prior will be used to determine posterior probabilities of harm from the intervention, $\Pr(\theta > 1 | X)$, as well as 95% credible intervals.

For ordinal safety outcomes, the estimated posterior distribution odds ratio for the cumulative logits, ϕ , will be estimated based on the data and the neutral prior. In addition, posterior probabilities of harm, $\Pr(\phi > 1 | X)$, and 95% credible intervals of ϕ will be calculated.

For count type safety outcome, the estimated posterior distribution of the treatment mean rate, ϕ , will be estimated based on the data and the neutral prior. In addition, posterior probabilities of harm, $\Pr(\phi > 1 | X)$, and 95% credible intervals of ϕ will be calculated.

Analysis of Ultrasound, CT scan, MRI and encephalopathy outcomes

Ultrasound, CT scan, MRI, and encephalopathy outcomes will be analyzed using the FAS population. Head ultrasounds, CT scans, and brain MRIs will be summarized by treatment and time (prior to intervention, during intervention, after intervention, any time). Summaries will be created for number of babies with any abnormal findings during time period data recorded, and for total events across all babies during any time period.

Normal/Abnormal findings in Ultrasound, CT scan, and MRI after intervention will be summarized by treatment. The summarized measure will be any normal/abnormal findings after intervention. In addition to normal/abnormal findings, the following abnormal findings will also be summarized by treatment with respect to any findings after intervention:

- 1) basal ganglia, thalamic abnormality, posterior limb of the internal capsule abnormality (based on MRI, conditions 3, 24 on PH12 form. Posterior limb of the internal capsule abnormality will be captured with condition 22 and other.)
- 2) white matter abnormality (based on MRI, condition 23 on PH12 form.)
- 3) IVH (based on MRI, conditions 5 and 6)
- 4) post-hemorrhagic ventricular dilatation or non-hemorrhagic ventricular dilatation (based on MRI, conditions 5, 6, and 17 on PH12 form.)
- 5) IVH (based on Ultrasound, conditions 5 and 6)
- 6) Any bleeding (based on MRI, conditions 4-10, 13, 14, 25, or 26 on PH12 form.)

Additional analyses of these outcomes will be covered under a separate SAP.

